10.4 DATA SOURCES

The study will utilize a data collection system implemented by the Sponsor, targeting patients who meet the eligibility criteria. Variables collected for the purpose of the study will be re-transcribed from existing electronic and/or paper medical records maintained at site. The PasTel study involves primary data collection in which the data collected are derived from routine clinical care. In instances where patient recruitment or follow-up activities specific to evaluating the safety of TachoSil exposure, extend beyond the regular routine activities at the study site, additional data will be collected by personnel at the participating study site. This primary data collection will be incorporated into the case report forms (CRFs)

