10. RESEARCH METHODS

10.1 STUDY DESIGN

This is a prospective, multicentre, non-interventional, uncontrolled, observational, post-authorization cohort study aimed at investigating the short- and long-term safety of TachoSil application.

The study will enrol patients undergoing cardiovascular, hepatic or other solid organs surgery, as well as those with injuries of blood vessels, parenchymal organs, lungs requiring the use of drugs for local haemostasis, tissue sealing, and suture support in vascular surgery where standard techniques are insufficient and where TachoSil was used as a secondary haemostatic treatment. The cohort will include patients identified by participating investigators (prospective enrolment). Patients who meet specified inclusion/exclusion criteria and their legal representatives will receive comprehensive information about the study orally and in written form, tailored to their understanding. The investigator will obtain their voluntary, personally signed, and dated informed consent before collecting any study-related information.

Short-term safety data, including adverse events (AEs) and adverse events of special interest (AESIs), will be collected prospectively from the time of informed consent signature, during hospital stay, and until hospital discharge. Time to onset (TTO), duration, severity, outcome, treatment and relatedness to TachoSil will be analyzed for reported AEs and AESI.

All enrolled patients will be followed for up to 36 months after surgery to monitor long-term treatment-related events and their clinically significant consequences.

To minimize stress for patients and caregivers associated with the study and the surgical intervention itself, the number and frequency of follow-up visits during the observation period will align with the routine follow-up procedures of the clinical sites.

Primary endpoint:

1. The proportion of subjects experiencing clinically significant local reactions including abscesses, hematoma formation or foreign body granuloma formulation, at the site of TachoSil application from the start of surgery up to 36 months post-surgery, as detected through routine imaging examinations (X-ray, ultrasound, CT, MRI or intraoperative detection or physical examination).

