Follow-up phase: The study phase is scheduled to last for up to 36 months following the date of surgery for each enrolled patient. There are six planned follow-up visits: one at 1 month (\pm 15 days) after surgery, another at 3 months (\pm 15 days), a third at 6 months (\pm 15 days), and a fourth, fifth and sixth visits at 12, 24 and 36 months (\pm 30 days) post-surgery, respectively. However, to minimize stress for patients and caregivers associated with the study and the surgical intervention itself, the number and frequency of follow-up visits during the observation period can be align with the routine follow-up procedures of the clinical sites.

The follow-up visits can be conducted in person at the study site if such visits are routinely performed, or they can take the form of telephone interviews with the patient and/or patient

PasTel

legal representative conducted by the Investigator. In both cases eCRF should be completed with all collected and required by Protocol data.

Patients have the right to discontinue their participation in the study at any time and for any reason, whether specified or unspecified.

Furthermore, a patient/legal representative (if applicable) may be withdrawn from the study if the Investigator determines that the patient no longer meets any of the inclusion/exclusion criteria.

Lost-to-follow-up (LTFU)

To ensure the smooth progress of the PasTel study, it is crucial to minimize the occurrence of lost-to-follow-up (LTFU). Loss-to-follow-up refers to patients and/or their legal representative who, at some point during the study, cannot be reached for further follow-up procedures, resulting in an unknown status and the inability to collect important long-term information, including adverse events. On the other hand, "dropout" refers to patients who voluntarily withdraw from the study, with their health status known upon departure.

To minimize lost-to-follow-up, the following follow-up process will be implemented: If a study participant (or their legal representative) does not respond to the initial telephone contact, up to two reminder calls will be made. If there is still no response after three phone calls, the participant will be sent an email or certified letter. The overall objective is to keep the loss-to-follow-up rate below 10 %. Based on the Corza Medical experience and Feasibility analysis, it is anticipated that the final LTFU will be approximately 10 %.

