Despite these strengths, PasTel study has also some limitations. The study does not include a control group for comparison. Without a control group receiving an alternative treatment or a placebo, it may be challenging to attribute observed outcomes solely to the TachoSil application. The absence of a control group limits the ability to establish causality or make direct comparisons. PasTel study relies on patient self-reporting during follow-up visits, which may introduce recall bias or incomplete data. Depending on the method of follow-up (in-person or telephone visits), the accuracy and reliability of the information collected may vary. Confounding by indication is also very common in observational studies (e.g., cohort studies). It can occur in relation to either beneficial outcomes or harmful outcomes and can result in either an increase or a reduction in the apparent risk of the outcome. However, careful study design, e.g., including a range of different indications for the same exposures, enables the relationship between the exposure and the outcome in relation to each of the individual indications to be analysed separately. A consistent outcome across all indications will suggest that the outcome is indeed due to the exposure, since it is unlikely that each different indication would cause the same outcome.

The study design may be prone to selection bias, primarily due to its non-interventional, observational nature and specific inclusion/exclusion criteria. By focusing only on paediatric patients undergoing certain types of surgery and requiring specific haemostatic treatments, the study might not represent the broader paediatric population undergoing various surgical

PasTel

procedures. Additionally, excluding patients with congenital disorders of haemostasis or severe coagulopathy could further skew the results, as these patients might exhibit different safety profiles or adverse event rates. These selective criteria can impact the generalizability of the study findings to all paediatric surgical patients.

Finally, participants have the option to withdraw from the study at any time, which could lead to attrition bias if those who withdraw differ systematically from those who remain. Additionally, discontinuation may result in incomplete data for some patients, potentially affecting the overall study findings.

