- Recovering/Resolving: Condition is improving, and patient is expected to recover from the event
- Recovered with sequelae: As a result of the AE, the patient suffered persistent and significant disability/incapacity (e.g., became blind, deaf or paralyzed)
- Not recovered
- Fatal
- Unknown.

Reporting of adverse events

Throughout the conduct of the study, the Principal Investigator and investigators will be responsible for collecting and reporting adverse events to the Sponsor (Corza Medical). They are responsible for the timely identification, documentation, and reporting of all AEs, AESIs and adverse reactions (ARs) observed during the study. The principal investigator will ensure that all investigators are thoroughly trained in these procedures and understand their responsibilities.

The management of the follow-up of AEs and ARs, including reporting to the sponsor, is a critical component of the study. Investigators are required to provide comprehensive follow-up information on each AE and AR, ensuring detailed documentation of the event's evolution, management, and resolution. This information must be communicated to the sponsor promptly as per the reporting timelines outlined in the protocol. All events that met the definition of an AE and will occur in the period from the patient signing the ICF and until the final follow-up visit (at 36 month \pm 30 days) will be recorded. During follow-up phase of the study, at each contact between the study site and the patient (visit or phone), the patient will be asked no leading questions about AEs, e.g., "Have you experienced any problems since our last contact?"

The investigator will record all AEs on the standard AE Form (electronic CRF). The investigator will record only 1 AE per form.

For SAE/s, the SAE Form (electronic CRF or paper SAE Form if eCRF is out of order) will also be completed. The investigator will have to record the diagnosis if available. If no diagnosis is available, the investigator will record each sign and symptom as individual AEs. The investigator will evaluate the seriousness, severity, outcome, and causality of AEs.

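### No follow-up contact asks about care at other hospitals and no step obtains their findings, so the 36-month proportion risks under-ascertainment of unknown size, probably downward

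*Protocol*

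**What the plan says.** Section 10.4 of the protocol names the main source: "Variables collected for the purpose of the study will be re-transcribed from existing electronic and/or paper medical records maintained at site". It then adds a second route: where recruitment or follow-up activities "extend beyond the regular routine activities at the study site, additional data will be collected by personnel at the participating study site".

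Section 10.2 plans contacts at 1, 3, 6, 12, 24 and 36 months. Visits are in person where that is routine; otherwise "they can take the form of telephone interviews with the patient" or the legal representative. The number and frequency of visits may follow site routine. Section 10.3 lists, for every follow-up contact, adverse events and their treatment, AESIs, concomitant therapies, comorbidities, and an item for granuloma, adhesions and other endpoint events. Table 5 qualifies the collected data as being subject to availability.

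On elicitation, section 12 says that "at each contact between the study site and the patient (visit or phone), the patient will be asked no leading questions about AEs", with one open example about problems since the last contact. Once an event is known, "Investigators are required to provide comprehensive follow-up information on each AE and AR, ensuring detailed documentation of the event's evolution, management, and resolution".

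Section 10.1 defines the primary endpoint as clinically significant local reactions up to 36 months "as detected through routine imaging examinations (X-ray, ultrasound, CT, MRI or intraoperative detection or physical examination". Section 10.9 concedes that the "PasTel study relies on patient self-reporting during follow-up visits, which may introduce recall bias or incomplete data". It does not mention care given elsewhere.

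**The concern.** About four centres follow children for three years, and the last three contacts are a year apart. A late abscess, haematoma or granuloma may be imaged, treated or operated on at a hospital nearer home. That event is not in the site's own record unless someone brings it there, so it depends on the family raising it in reply to an open question, possibly by telephone and up to a year later. If it is raised, a telephone call cannot supply the imaging, operative or examination findings on which the endpoint rests, and the protocol does not say how they are to be obtained.

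This affects the evidence that the study exists to provide. Its purpose is to fill a gap on long-term and delayed effects. It is uncontrolled, so no comparator arm shares the under-count, and section 10.7 plans to set the results beside published ones. In the dataset, a missed late event looks the same as a good outcome.

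**Working it through.** **1. The plan's own figures.** Section 10.2 gives 66 recruited, 10% dropout and at least 60 analysable. 66 × 0.90 = 59.4, which agrees to rounding. These figures are not in dispute, and n = 60 is used below. The protocol states no expected event rate or precision target.

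**2. The routes by which an event treated elsewhere could reach the analysis.**

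| Route | Would it bring the event in? |
|---|---|
| Transcription of site records (10.4) | Only if the other hospital's papers are already in the site file |
| Additional data collected by site staff (10.4) | Possible, but no outside source is named |
| Endpoint item at each contact (10.3) | Yes, if the family knows of it and says so; no question on care elsewhere |
| Open adverse event question (12) | Yes, if volunteered |
| Serious adverse event form and follow-up duty (12) | Yes, once the event is known; no way of obtaining outside reports is given |
| Completeness and consistency checks (10.8) | No; these test what was entered, not what was missed |

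So the event can be recorded. What is missing is a prompt that finds it and a step that documents it.

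**3. Illustration of size. Every input here is an assumption, none is in the protocol.** Let p be the true 36-month proportion, d the share of events arising after discharge, e the share of those managed elsewhere, and c the share of these that are captured. If no false reports are counted,

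observed = p × [1 − d × e × (1 − c)].

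For p = 10% (6 events expected in 60) and d = 1:

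| e | c = 0 | c = 50% | c = 80% | c = 100% |
|---|---|---|---|---|
| 10% | 9.0% | 9.5% | 9.8% | 10% |
| 25% | 7.5% | 8.75% | 9.5% | 10% |
| 50% | 5.0% | 7.5% | 9.0% | 10% |

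Taking d = 1 is the least favourable choice, because the endpoint starts at surgery and some haematomas and abscesses will occur before discharge. With d = 0.5 each loss halves: for e = 50% and c = 50%, 10% × (1 − 0.5 × 0.5 × 0.5) = 8.75% instead of 7.5%.

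**4. Effect on a reassuring result.** With 0 events in 60, the exact upper 95% limit is 1 − 0.025^(1/60) = 5.96%, or 6.0%. If only a fraction s of all events is captured, the corresponding limit for the true proportion is 5.96%/s. If the true proportion is 5%, the chance of seeing no event is (1 − 0.05s)^60.

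| s | Upper limit | Chance of 0 in 60 at a true 5% |
|---|---|---|
| 100% | 6.0% | 4.6% |
| 90% | 6.6% | 6.3% |
| 75% | 8.0% | 10.1% |
| 50% | 11.9% | 21.9% |

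**5. Comparison with sampling error.** For 6 of 60 the exact 95% interval is 3.8% to 20.5%. Most losses in the table in step 3 are small beside that width. They differ in kind, though, because the interval does not reflect them.

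**The case against.** The strongest case on the other side is that the protocol does more than copy site records. Section 10.4 itself adds primary data collection. Section 10.3 requires an endpoint item at every contact. Section 12 makes any inpatient hospitalisation a serious adverse event, wherever it occurs, and demands comprehensive follow-up, which would ordinarily lead an investigator to ask for the discharge papers. The endpoint wording does not require detection at the study site or that the site hold the report. Clinical significance is left to the investigator's opinion and admits impairment reported by the patient. Section 10.9 discloses the reliance on self-report, section 10.2 excludes children at known risk of loss to follow-up and sets out reminder calls and letters, and the design deliberately limits the burden on families.

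Most of this stands, and it rules out a stronger reading. A reader might infer that outcomes come only from site records and that the 36-month proportion is therefore biased low. The documents do not support that: families can report outside events, such events can be counted, and unverified reports accepted as events could offset some of the loss. Nor do they support the inference that consent to obtain outside reports is lacking or that the gap could not be closed later. Section 11 is silent, but the consent pages are not in the review copy, and families can be asked at any of six contacts.

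What these safeguards leave open is narrower. The follow-up duty begins only when the event is known, and nothing prompts the family about care elsewhere or says how the outside findings are obtained.

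**Conclusion.** The point holds as a risk of under-ascertainment. Events treated elsewhere may go unreported or stay unconfirmed, and the error in the 36-month proportion is probably downward. Its size is unknown, because the protocol gives neither the share of care delivered elsewhere nor the share that contacts would capture. Over the assumed ranges in the working, the relative loss runs from nil to 50%; the upper end needs half of all events to be managed elsewhere and none of those captured. These figures illustrate sensitivity and do not estimate bias. The point is worth acting on because the study is uncontrolled, its purpose is late safety, a low or zero count will be read as reassurance, and the remedy is small. Data source, contact content and eCRF fields are protocol matters.

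**What to change.** In sections 10.2 and 10.3, add one fixed item to every follow-up contact, in person or by telephone: since the last contact, has the child had any hospital stay, imaging, operation or treatment of the operated region at another facility, and if so where and when? It can follow the open adverse event question, so that the non-leading opening is kept.

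If the answer is yes, request the discharge, imaging or operative report through the family, and confirm that the informed consent form permits this. Add an eCRF field for the source of each endpoint event: site, other facility, or family report only. Show the primary endpoint with and without events supported by family report only; the layout of that display can be left to the SAP. Add care received elsewhere to the limitations in section 10.9.

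The cost is one question per contact for about 66 children, one eCRF field, a check of the consent wording, and some site time to request letters for those treated elsewhere.

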10.5 STUDY SIZE

Approx.4 or more, if required, paediatric surgery centres will participate in the PasTel study.

Based on feasibility assessments, approximately 66 patients are expected to qualify for the study and undergo surgery. All patients who undergo surgery will be included in the analysis. An anticipated dropout rate is 10 %.

The recruitment will be conducted until the planned number of patients is reached. All patients available in the study population will be considered for the analysis.

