10.2 SETTINGS

The study will include approx. 4 sites or more, if required (Table 1). Estimated total number of recruited patients is 66. Based on feasibility assessments, approximately 66 patients are expected to qualify for the study and undergo surgery. All patients who undergo surgery will be included in the analysis. An anticipated dropout rate is 10%. Finally, number of subjects eligible for analysis: sample size is expected to be at least 60. The prospective recruitment of patients, by enrolling patients who have planned surgery and meet enrolment criteria will last for 12 months from the study start. All recruited patients will be followed up to 36 months after the date of the surgery.

Note: in emergency situation that requires acute surgery with TachoSil application, obtaining informed consent and including the patient in the study after surgery may be considered, if legal and ethical requirements are met.

The study population is paediatric patients undergoing a cardiovascular, hepatic or other solid organs surgery and polytrauma with injuries of blood vessels, parenchymal organs, lungs requiring the use of drugs for local haemostasis, tissue sealing when control of bleeding by standard surgical techniques (such as suture, ligature, clips or cautery) appeared to be ineffective or impractical.

PasTel

Data will be collected from the following age groups :

- Infants and toddlers (≥ 28 days - < 2 years) on the day of signing the ICF
- Children (≥ 2 years – < 12 years) on the day of signing the ICF
- Adolescents (≥ 12 years – less than 15 years) on the day of signing the ICF

Patient age analysis will be conducted throughout the study to ensure a proportional number of participants in each of the three age groups (if possible, approx. 33% per group). Ensuring an adequate number of participants in each age group will ensure that data are collected across a broad paediatric population to assess short- and long-term safety evaluation.

Inclusion/Exclusion criteria

The study population covers paediatric patients undergoing a cardiovascular, hepatic or other solid organs surgery, and polytrauma patients with injuries of blood vessels, parenchymal organs, lungs requiring the use of drugs for local haemostasis, tissue sealing when control of bleeding by standard surgical techniques (such as suture, ligature, clips or cautery) appeared to be ineffective or impractical (secondary haemostatic treatment).

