Data will be collected from the following age groups:

- Infants and toddlers (≥ 28 days - < 2 years) on the day of signing the ICF
- Children (≥ 2 years – < 12 years) on the day of signing the ICF
- Adolescents (≥ 12 years – less than 15 years) on the day of signing the ICF

Inclusion criteria

The following individuals are eligible to participate:

- Patients aged from ≥ 28 days to < 15 years on the day of signing the ICF.

Important Note: According to legal regulations in Poland, patients who are 18 years of age or older cannot be treated by paediatric surgeons. Therefore, only patients who are under 18 years of age by the end of the observation period will be included in the study.

- Patients who have planned a cardiovascular, hepatic or other solid organs surgery and polytrauma patients with injuries of blood vessels, parenchymal organs, lungs qualified for elective surgery
- Patients planned to have at least one TachoSil matrix applied (intraoperatively) and without the plan of application of any other products for local haemostasis at the place of TachoSil application will be qualified for the study.

Exclusion Criteria

The following individuals are not eligible to participate:

- they have known, recognized earlier congenital disorders of haemostasis such as haemophilia type A,B,C, Marfan syndrome, Rendu-Osler-Weber disease, congenital thrombocytopathies, e.g. Glanzmann's thrombasthenia, von Willebrand disease type 1,2,3, Fanconi's anaemia.

PasTel

- they have experienced severe coagulopathy defined as: INR >2.0, platelet count (PLT)<50 000 / mm³; APTT>60 seconds in the period from 7 days before to the day of surgery.
- they are hypersensitive to the active substance(s) or to any of the product excipients.
- female patients of childbearing potential: they are pregnant or want to become pregnant or those who do not use sufficient methods of contraception such as contraceptive implant, intrauterine coil and oral hormonal contraception.

The patient who, in the investigator's opinion, presents a known risk of being lost to follow-up during the 36-month follow-up period, based on the screening assessment.

The study period will be divided into enrolment phase and follow-up phase. Both study phases can last simultaneously.

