Enrolment phase: The duration of this study phase is set to be 12 months, starting from the commencement of the study at each individual site. The center will be able to start recruiting patients after obtaining, accepting and signing all necessary documents to conduct an observational study in accordance with the regulations of Polish law. The Sponsor will communicate the study start date to the sites through email and telephone contact. Patient enrolment will be carried out amongst those scheduled for upcoming surgeries.

Patients who are scheduled to undergo cardiovascular, hepatic, or other solid organ surgeries, as well as polytrauma with injuries to blood vessels, parenchymal organs, or lungs, will be identified by the designated Investigator during their routine visit to the study site. During this visit, the Investigator will discuss the study details with the patient and/or their legal representative and ask for their willingness to participate. If the patient meets the remaining inclusion/exclusion criteria, including the intraoperative application of at least one TachoSil patch, they will be enrolled in the study. It's important to note that the participating sites will use TachoSil as part of their routine clinical practice in the specified indications mentioned above. TachoSil itself is not considered an intervention in the study; its application during surgery is one of the inclusion criteria. The day on which informed consent is obtained will be considered a screening visit.

For all enrolled patients, they will continue following the routine procedures of the study site leading up to the day of surgery and throughout their hospital stay until discharge. The Investigator will perform safety assessments during the perioperative period, which includes the time from the day of surgery until discharge. These assessments will involve monitoring adverse events (AEs), adverse events of special interests (AESIs), vital signs (blood pressure, heart rate, temperature), and the analysis of relevant clinical laboratory variables as part of the routine procedure (morphology, INR, APTT).

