10.7 DATA ANALYSIS

All analyses will be performed for the study population, which will comprise all enrolled subjects who received at least 1 application of TachoSil. Study endpoints will be summarised by descriptive statistics. For primary and secondary endpoints, rate of occurrence and cumulative incidence of AEs and AESIs will be determined. Time to onset (TTO), duration, severity, outcome, treatment and relatedness to TachoSil will be analyzed for reported AEs and AESI.

Descriptive statistics of all endpoints may include specifically but not exclusively, arithmetic mean, medians, standard deviations, proportions, frequency counts and 25th and 75th percentiles. Where applicable, 95% confidence intervals of select point estimates will be determined. Figures will be prepared to illustrate the patterns of data over time where appropriate. The number of subjects included in each analysis set will be reported.

A qualitative comparison of results collected during the study with an existing literature data will be performed, particularly focusing on the incidences, time to onset, severity, and outcomes of AESIs and SAEs, with existing literature. Literature searches in databases like PubMed, Embase and Cochrane Library will be conducted to identify relevant studies. The search will use specific keywords and criteria related to TachoSil, adverse events, and study

populations.- Studies selected for comparison will be based on relevance, quality, and up to date results. Key data from the selected studies, such as incidences, time to onset, severity, and outcomes of AESIs and SAEs, will be extracted. A standardized form will be used to ensure consistent data collection. A narrative synthesis will be provided, discussing similarities and differences in the findings. Both our study and the selected literature will undergo a critical appraisal to assess the quality and risk of bias, which will be considered in the interpretation of the results. The discussion will highlight the similarities and differences in the findings to provide context for the study's outcomes. Additionally, the Clinical Study Report will include a description of the methodology utilized, including search keywords, inclusion and exclusion criteria for relevant studies, and data collection form used in the analysis.

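### The protocol defines the analysis population in two conflicting ways, all operated children and TachoSil recipients only, and the first would understate the primary endpoint if any operated child receives no patch

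*Protocol*

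**What the plan says.** **Analysis population.** Section 10.5 says "All patients who undergo surgery will be included in the analysis". The same sentence stands in section 10.2 and under the study size heading of the Abstract. Section 10.7 says "All analyses will be performed for the study population, which will comprise all enrolled subjects who received at least 1 application of TachoSil", and the Abstract repeats this under its data analysis heading. The Abstract therefore carries both rules in consecutive paragraphs.

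**Eligibility.** The inclusion list in section 10.2 (also in the Abstract) admits "Patients planned to have at least one TachoSil matrix applied (intraoperatively) and without the plan of application of any other products for local haemostasis" (the last part refers to the application site). The enrolment-phase text of section 10.2 instead treats the event itself as the condition. A child who meets the remaining criteria, "including the intraoperative application of at least one TachoSil patch, they will be enrolled in the study", and later: "TachoSil itself is not considered an intervention in the study; its application during surgery is one of the inclusion criteria".

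**Timing and place in treatment.** Section 10.2 describes the product as second-line, for cases where standard techniques "such as suture, ligature, clips or cautery) appeared to be ineffective or impractical (secondary haemostatic treatment". Consent normally precedes surgery. An emergency note in section 10.2 allows consent afterwards when TachoSil was applied.

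**Numbers.** Section 10.2 gives about 66 patients expected to qualify and undergo surgery, 10% dropout, and at least 60 for analysis.

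**The concern.** The protocol fixes the denominator of its primary endpoint twice, with different results, so the author of the analysis plan could cite either rule. This is not a detail that the protocol leaves open for later.

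The two rules differ only if an enrolled child is operated on without receiving a patch. That is foreseeable. Enrolment usually rests on a plan made before surgery, while the need for a second-line product becomes clear during it. The protocol does not say what happens to such a child.

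The primary endpoint is a reaction at the TachoSil site, which cannot occur without a patch. Counting children who could not have the event pushes the result towards apparent safety, in a study meant to estimate the frequency of adverse reactions in exposed children. The number of exposed children, which sets the precision, would also be unknown.

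**Working it through.** **1. The plan's own figure.** Inputs from section 10.2: 66 patients, 10% dropout, at least 60 analysed.
- Forward: 66 × 0.90 = 59.4, in effect 60.
- Backward: 60 / 0.90 = 66.7, rounded up to 67; or 60 × 1.10 = 66.

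The figure reproduces, and dropout accounts for the whole step. Section 10.2 defines dropout as voluntary withdrawal, so no allowance for non-use is visible.

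**2. Events that need a patch.** These are the primary endpoint, adverse events related to the product, and infections at the application site (as worded in section 10.1). Let s be the share of operated children without a patch. Then

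proportion(all operated) = proportion(exposed) × (1 − s).

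The protocol gives no s. I assume 0 to 30%, where 0% is the result if actual application is enforced as a criterion. The 10% risk and the four events below are also illustrations. Intervals are exact (Clopper-Pearson) 95%.

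| s | Unexposed / exposed of 66 | A 10% risk in the exposed is reported as | 4 events, exposed only | 4 events, all operated | Upper limit with 0 events, exposed only |
|---|---|---|---|---|---|
| 0% | 0 / 66 | 10% | 6.1% (1.7–14.8) | 6.1% (1.7–14.8) | 5.4% |
| 10% | 7 / 59 | 9% | 6.8% (1.9–16.5) | 6.1% (1.7–14.8) | 6.1% |
| 20% | 13 / 53 | 8% | 7.5% (2.1–18.2) | 6.1% (1.7–14.8) | 6.7% |
| 30% | 20 / 46 | 7% | 8.7% (2.4–20.8) | 6.1% (1.7–14.8) | 7.7% |

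If no event is seen, the all-operated rule always gives an upper limit of 5.4%, although the exposed group may support only 7.7%.

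**3. Events that can occur without a patch.** These include thrombotic events, allergic reactions, bleeding at the surgical site, and adhesions as a finding. Here

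proportion(all operated) = p_exposed × (1 − s) + p_unexposed × s.

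The direction depends on the unexposed rate. To show this, I borrow pairs of percentages from Table 4 and set s = 20%. The comparator children there received another haemostatic product, so these are not forecasts.
- Fall: 44.4% and 33.3% give 0.8 × 44.4 + 0.2 × 33.3 = 42.2%.
- No change: 22.2% and 22.2% give 22.2%.
- Rise: 5.6% and 33.3% give 0.8 × 5.6 + 0.2 × 33.3 = 11.1%.

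**The case against.** The strongest reply is that the intended rule is clear enough. Section 9 names exposed children as the target population. Section 10.7 says that all its analyses use recipients. Section 10.5 itself ends by referring to the study population, which section 10.7 defines as exposed only. If the enrolment-phase text is followed and application is a criterion, every qualifying child is exposed and the two rules coincide. Table 5 appears to support this by marking the eligibility check at surgery as well as at screening. The study is descriptive, with no hypothesis test.

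Much of this stands: exposed-only is the likelier intention, and s may be zero. It does not remove the conflict. The all-operated sentence appears three times, and the listed inclusion criterion asks only for planned use. Section 10.2 says that a patient who no longer meets the criteria may be withdrawn, which is permissive, while section 10.1 has all enrolled patients followed for up to 36 months.

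A reader might infer more than the protocol supports:
- *Every safety proportion is diluted.* Only events that need a patch must fall. For the others the direction is unknown, although the adhesion definition carries some product-attribution wording.
- *Some operated children will certainly have no patch.* No non-use rate is given, and children who enter by the emergency route have already received TachoSil.
- *Recruitment stops at 66 operated children.* Section 10.5 says only that recruitment runs until the planned number is reached, without saying what is counted.
- *Unexposed children will be followed for 36 months to no purpose.* The withdrawal provision is a possible route out, and whether to follow them is a design preference.

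**Conclusion.** The point holds as an internal contradiction about the primary denominator, together with a second contradiction about eligibility that decides whether the first one matters. The all-operated rule is wrong as written for endpoints that need a patch, and its error is always towards fewer events. The size cannot be derived from the protocol. For an assumed non-use share of 0 to 30%, the relative understatement is 0 to 30%, and 66 operated children include 66 to 46 exposed. The surgical-site bleeding, thrombotic, allergic and adhesion results need not be understated. Section 7 plans the start of data collection for 3Q 2026, so the wording can be settled before the first child is enrolled.

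**What to change.** 1. In the Abstract and in sections 10.2 and 10.5, replace the all-operated sentence with the section 10.7 set, for example: *The analysis population is the enrolled patients with one or more TachoSil applications, as defined in section 10.7.*
2. Reconcile the planned-use criterion in the inclusion list with the actual-application wording of the enrolment-phase text in section 10.2.
3. State whether 66 and at least 60 count operated or exposed children. If they count operated children, give the expected number exposed and the non-use share assumed.
4. Report children who were enrolled and operated on but received no patch separately, outside all endpoint denominators.

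**Cost.** No new data are needed, but this is a protocol amendment. Under section 10.8 it goes to the ethics committee, the national authority and the EMA for approval. The stated analysis number may become smaller: at 30% non-use, 46 exposed before any dropout, against the stated minimum of 60.
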